6.1 Full Analysis Set

Not applicable.

6.1.1 Primary Analysis Set

Not applicable.

6.2 Safety Analysis Set

Safety analysis set consists of all subjects who received at least 1 dose of tarlatamab.

The analysis of all safety endpoints and efficacy endpoints, unless noted otherwise, are conducted using safety analysis set.

6.3 Per Protocol Analysis Set(s)

Not applicable.

6.4 Health-related Quality-of-Life or Health Economics Analyses Set(s)

Not applicable.

6.5 Pharmacokinetic/Pharmacodynamic Analyses Set(s)

Pharmacokinetic (PK) analysis set consists of all subjects who received at least 1 dose of tarlatamab and have at least 1 pharmacokinetic sample collected. These subjects are evaluated for PK analysis unless the number of data points required for analysis is not enough, or significant protocol deviations have affected the data, or if key dosing or sampling information is missing. Analysis of PK data, unless otherwise specified, is conducted using pharmacokinetic analysis set.

6.6 Interim Analyses Set(s)

Not applicable

6.7 Study-specific Analysis Set(s)

6.7.1 RECIST 1.1 Evaluable by Blinded Independent Central Reviewer Analysis Set

RECIST 1.1 evaluable by blinded independent central reviewer analysis set consists of all subjects who received at least 1 dose of tarlatamab, have measurable baseline disease per RECIST 1.1 as assessed by blinded independent central reviewer. This analysis set is used for RECIST 1.1 related endpoints assessed by central reviewer for sensitivity analyses.

7. Planned Analyses

7.1 Interim Analysis and Early Stopping Guidelines

Not applicable.

7.2 Primary Analysis

The primary analysis is planned **after** all subjects have been enrolled and have had opportunity to **confirm an objective response** after **the** first post-treatment scan **or up to 13 weeks of follow-up, whichever occurs first**

The data will be subject to ongoing checks for integrity, completeness, and accuracy in accordance with the Data Management Plan. The data supporting the primary analysis will be locked. It is expected that outstanding data issues are resolved ahead of the lock to the extent possible.

7.3 Final Analysis

The final analysis will occur when enrollment is complete and each subject completes the study, including long-term follow-up.

The data will be subject to ongoing checks for integrity, completeness, and accuracy in accordance with the Data Management Plan. The data supporting the final analysis will be locked to prevent future changes. It is expected that all outstanding data issues are resolved ahead of the final lock.

8. Data Screening and Acceptance

8.1 General Principles

The objective of the data screening is to assess the quantity, quality, and statistical characteristics of the data relative to the requirements of the planned analyses.

8.2 Data Handling and Electronic Transfer of Data

The Amgen Global Study Operations-Data Management (GSO-DM) department will receive and store all data to be used in the planned analyses. This study will use the RAVE database.

8.3 Handling of Missing and Incomplete Data

Partially missing dates for adverse event, concomitant medication, new anti-cancer therapy initiation and death will be imputed as outlined in [Appendix A](#).

8.4 Detection of Bias

Lack of protocol compliance and the potential for biased statistical analyses will be examined by assessing the incidence of important protocol deviations (IPD). The clinical study team will identify and document the criteria for important protocol deviations.

8.5 Outliers

Descriptive statistics will be used to identify potential outliers in key variables. Suspected outliers will be included in all analyses unless there is sufficient scientific justification to exclude them.

8.6 Distributional Characteristics

The assumptions underlying the proposed statistical methodologies will be assessed as appropriate. If required data transformations or alternative non-parametric methods of analyses will be utilized.

8.7 Validation of Statistical Analyses

Programs will be developed and maintained and output will be verified in accordance with current risk-based quality control procedures.

Tables, figures, and listings will be produced with validated standard macro programs where standard macros can produce the specified outputs.

The production environment for statistical analyses consists of Amgen-supported versions of statistical analysis software; for example, the SAS System version 9.4 or later.

9. Statistical Methods of Analysis

9.1 General Considerations

Descriptive statistics will be provided for selected demographics, safety. Descriptive statistics on continuous data will include means, medians, standard deviations, and ranges, while categorical data will be summarized using frequency counts and percentages. Graphical summaries of the data may also be presented.

For proportions, 95% CI will be estimated using an exact method proposed by Clopper-Pearson (Clopper and Pearson, 1934). Kaplan-Meier methods will be used to estimate the median and percentiles for time-to-event endpoints with CI calculated using the Brookmeyer and Crowley (Brookmeyer and Crowley, 1982) method. Kaplan-Meier methods will be used to estimate landmarks for time-to-event endpoints (eg, 1-year OS) with the Greenwood formula (Kalbfleisch and Prentice, 1980) used to estimate the standard error used in CI calculation. Kaplan-Meier curves will be constructed for time-to-event endpoints.

9.2 Participant Accountability

The number and percent of subjects who were enrolled, received investigational product, completed investigational product, discontinued from investigational product (including reasons for discontinuation), completed study, discontinued the study (including reasons for discontinuation) will be summarized. Key study dates for the first subject enrolled, last subject enrolled, and last subject's end of study will be presented.

9.3 Important Protocol Deviations

Important protocol deviations (IPD) categories are defined by the study team before the

first subject's initial visit and will be updated during the IPD reviews throughout the study prior to database lock. These definitions of IPD categories, subcategory codes, and descriptions will be used during the course of the study. Eligibility deviations are defined in the protocol.

The final IPD list is used to produce the summary of IPDs table and the list of subjects with IPDs. In addition, a separate listing of all inclusion and exclusion deviations may be provided.

9.4 Demographic and Baseline Characteristics

Descriptive summaries of the demographic and baseline characteristics will be produced for the following based on the safety analysis set:

- Race. If multiple races have been reported for a subject, the subject will be categorized as 'Multiple'
- Sex
- Age at enrollment in years
- ECOG performance status at baseline
- Weight (kg)
- Height (cm)
- BMI (kg/m²)
- Time from initial diagnosis to enrollment (months)
- Prior lines of therapy
- Metastatic
- Sum of diameters of target lesions at baseline based on investigator assessment (mm)

9.5 Efficacy Analyses

The following efficacy analysis will be performed.

9.5.1 Analyses of Primary Efficacy Endpoint(s)/Estimand(s)

Table 9-1. Example Primary Efficacy Endpoint/Estimand Summary Table

Endpoint/Estimand	Primary Summary and Analysis Method	Sensitivity Analysis
ORR based on BICR	Proportion of subjects with OR, corresponding Clopper-Pearson (Clopper and Pearson, 1934) exact 95% CI.	Repeat summary on RECIST 1.1 evaluable by blinded independent central reviewer analysis set.

The efficacy analyses of primary endpoint will be conducted on the safety analysis set, unless otherwise specified. the proportion of subjects with a BOR of PR or better per RECIST 1.1 based on BICR with corresponding Clopper-Pearson 95% CI will be Presented.

9.5.2 Analyses of Secondary Efficacy Endpoint(s)/Estimand(s)

Table 9-2. Example Secondary Efficacy Endpoint/Estimand Summary Table

Endpoint/Estimand	Primary Summary and Analysis Method	Sensitivity Analysis
DCR based on BICR	Proportion of subjects with DC, corresponding Clopper-Pearson (Clopper and Pearson, 1934) exact 95% CI.	Repeat summary on RECIST 1.1 evaluable by blinded independent central reviewer analysis set.
DoDC, DOR, PFS based on BICR	Distribution of DoDC, DOR, PFS, corresponding median and percentiles using Kaplan-Meier (KM) method with 95% CI calculated using the Brookmeyer and Crowley (Brookmeyer and Crowley, 1982) method.	Repeat summary on RECIST 1.1 evaluable by blinded independent central reviewer analysis set.
ORR, DCR based on investigator assessment	Proportion of subjects with OR, DC, corresponding Clopper-Pearson (Clopper and Pearson, 1934) exact 95% CI.	None
DoDC, DOR, PFS based on investigator assessment	Distribution of DoDC, DOR, PFS, corresponding median and percentiles using Kaplan-Meier (KM) method with 95% CI calculated using the Brookmeyer and Crowley (Brookmeyer and Crowley, 1982) method.	None

Endpoint/Estimand	Primary Summary and Analysis Method	Sensitivity Analysis
OS	Distribution of OS, corresponding median and percentiles using Kaplan-Meier (KM) method with 95% CI calculated using the Brookmeyer and Crowley (Brookmeyer and Crowley, 1982) method.	None

The efficacy analyses of secondary endpoints will be conducted on the safety analysis set, unless otherwise specified.

For ORR based on investigator assessment, the proportion of subjects with PR or better and corresponding Clopper-Pearson 95% CI will be presented. For DCR based on BICR and DCR based on investigator assessment, the proportion of subjects with DC and corresponding Clopper-Pearson 95% CI will be presented.

The distribution of DoDC, DOR, and PFS (per RESIST 1.1 based on BICR) and the distribution of OS, including median and percentiles using Kaplan-Meier (KM) method with 95% CI calculated using the Brookmeyer and Crowley will be presented. Landmarks at selected time points (e.g. 3, 6, 9 and 12 months) with 95% CI calculated using the Greenwood formula (Kalbfleisch and Prentice, 1980) to estimate the standard error in CI calculation will be provided. For DoDC, percentages of subjects with DoDC ≥ 4 months will also be provided.

The distribution of DoDC, DOR and PFS per RESIST 1.1 based on investigator assessment will be summarized using the same methods as that of DoDC, DOR, and PFS (per RESIST 1.1 based on BICR) on safety analysis set. In addition, percent change from baseline in target lesion sum of diameters will be plotted for BICR and investigator assessment respectively.

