MRI brain	X ^f						X	All brain scans on protocol are required to be MRI unless MRI is contraindicated, then CT with contrast is acceptable. Subsequently after screening, MRI brain can be performed at any time if clinically indicated per standard of care.

Footnotes defined on last page of this table.

Table 1-1. Schedule of Activities: Cycle 1 only

Procedure ^a	Screening	Treatment Period ^b					As clinically indicated	Notes
		Cycle 1						
Day	(Up to 21 Days Before Day 1)	1	2	8	9	15		
Radiological imaging and tumor assessment ^g	X ^f	Weeks 1 to 48: Q6W (± 1 week) Weeks 49+ Q12W (± 1 week) by BICR per RECIST 1.1					X	Refer to Section 8.3.1 for additional details. For subjects who end study treatment for reasons other than specified in Section 8.3.2, every effort should be made to perform scheduled radiographic imaging (CT/MRI) until radiographic progression.
STUDY TREATMENT AND MONITORING								
Other protocol-required therapy: Dexamethasone		X		X				Refer to Section 6.1.2 for details for pre-treatment with dexamethasone (or equivalent dose of other corticosteroids). Dexamethasone will be administered within 1 hour prior to tarlatamab infusion on days 1 and 8 of cycle 1 only.
Tarlatamab Infusion		X		X		X		

Footnotes defined on last page of this table.

Table 1-1. Schedule of Activities: Cycle 1 only

Procedure ^a	Screening	Treatment Period ^b					As clinically indicated	Notes
		Cycle 1						
Day	(Up to 21 Days Before Day 1)	1	2	8	9	15		
Monitoring post-tarlatamab infusion		X		X			X	Subject will remain at study site for 6 to 8 hours post-infusion at C1D1 and C1D8 Cohabitant (caregiver) support for 24 hours post-infusion and the ability to stay within 1 hour of a hospital for 24 hours is required. Counseling the subject and caregiver on signs and symptoms of CRS and ICANS by a health care provider is required prior to discharge. Subjects return to site on C1D2 and C1D9 for vital signs and physical examination. At subsequent visits, additional monitoring may be recommended post-tarlatamab infusion based on occurrence of CRS, ICANS, or ICANS-related neurological events. Refer to Table 6-1 .
Other protocol-required therapy: IV hydration		X		X				Refer to Section 6.1.2 for details related to IV hydration. IV hydration (1 L normal saline) over 2 to 4 hours following tarlatamab administration.

Page 5 of 5

BICR = Blinded Independent Central Review; C1D1 = cycle 1 day 1; C1D2 = cycle 1 day 2; C1D8 = cycle 1 day 8; C1D9 = cycle 1 day 9;

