9.4.2.2 Efficacy Analyses

Endpoint/Estimand	Statistical Analysis Methods
Primary	
Objective Response Rate (ORR)	Summarized along with a Clopper-Pearson exact binomial CI. Subjects without a post-baseline tumor assessment will be considered non-responders.
Duration of Response (DOR)	Summarized with Kaplan-Meier estimate and 95% CI for quartiles and rates for select durations
Disease Control Rate (DCR)	Analyzed by the same methods used to analyze ORR. The summary of clinical benefit (ie, percentages of subjects with duration of disease control ≥ 4 months) will be provided. The percent change from baseline in target lesion sum of diameters will be plotted.
Progression-free survival (PFS)	Analyzed by the same methods used to analyze DOR
Overall Survival (OS)	Analyzed by the same methods used to analyze DOR

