2.2 Hypotheses and/or Estimations

No statistical hypotheses will be tested.

3. Study Overview

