3.2 Sample Size

Approximately 30 subjects will be enrolled in the study. With 30 subjects enrolled at the target dose, the probability that the observed ORR will be greater than **different thresholds are presented in Table 3.2-1.**

Table 3.2-1. Probabilities of Observed ORR Greater Than Thresholds With Sample Size of 30

True ORR	Probability of Observed ORR > 25 %	Probability of Observed ORR > 30%
0.35	88%	64%
0.4	96%	82%

With 30 subjects, there is a 79% to 96% probability of observing at least 1 adverse event if the true event rate is 5% to 10%.

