Appendix B. BOR per RECIST 1.1

BOR by investigator will be derived based on the timepoint response collected in the RECIST 1.1 CRF. BOR by central review will be derived from timepoint response shared by the central imaging vendor. At each time point, BOR will be derived based upon the evaluated timepoints up to and including the current MRI/CT assessment. The following rules will apply to BOR:

- CR is better than PR is better than SD is better than PD is better than NE
- For a BOR of SD, a duration of ≥ 35 days since the cycle 1 day 1 is required
- For a BOR of CR or PR confirmation is required. PR can be confirmed by a PR or CR. The confirmation assessment must be in a consecutive assessment ≥ 28 days after the initially observed assessment of CR or PR except the following cases:
 - An unlimited number of intermittent assessments of NE or CR <28 days can occur between the initial response and the confirmation of CR. For example, BL, CR, NE, NE, NE, CR – the CR at post-baseline 1 is confirmed at post-baseline 5. SD is not allowed between CR and subsequent confirmation CR.
 - An unlimited number of intermittent assessments of NE, SD, PR or CR <28 days can occur between the initial response and the confirmation of PR. For example, BL, PR, SD, SD, SD, PR – the PR at post-baseline 1 is confirmed at post-baseline 5.

[Table 14-2](#) provides the BOR determination per RECIST 1.1 where confirmation of response (CR/PR) is required. [Table 14-3](#) outlines the steps to derive Confirmed_BOR (step 1) given timepoint assessments.

At interim analyses (if any), due to lack of sufficient follow-up time for confirmation scan, study team may choose to report both confirmed responders and unconfirmed responders (subjects had an initial PR or CR and still has potential for future confirmative scans). Interim_BOR is defined to include unconfirmed responders in addition to those who achieve Confirmed_BOR. [Table 14-3](#) step 2 provides details to derive the unconfirmed responders.

Table 14-2. BOR per RECIST 1.1 where Confirmation of CR/PR is Required

Criterion	Timepoint T1 Response	T1 ≥ 35 days after C1D1?	Timepoint T2 Response	T2 ≥ 35 days after C1D1?	T2 ≥ 28 days after T1?	BOR_temp
C1	CR	Yes	CR	-	Yes	CR
C2			CR	-	No	SD
C3			PR, SD	-	-	Query data*

C4			PD	-	-	SD
C5			NE, No further evaluations			SD
C6		No	CR	-	Yes	CR
C7			CR	Yes	No	SD
C8			CR	No	No	NE
C9			PR, SD	-	-	Query data*
C10			PD	-	-	PD
C11			NE, No further evaluations			NE
C12	PR	Yes	CR, PR	-	Yes	PR

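### At the primary analysis the percentage with disease control of at least 4 months should be a Kaplan-Meier estimate, because the last enrollees have at most 13 weeks of follow-up

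*SAP*

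**What the plan says.** **The 4-month figure.** SAP 9.5.2 gives Kaplan-Meier medians, percentiles and landmarks with Greenwood intervals for duration of disease control (DoDC), naming 3, 6, 9 and 12 months as examples. It then adds "For DoDC, percentages of subjects with DoDC" of at least 4 months, with no estimator, denominator or rule for censored subjects. Protocol 9.4.2.2 has the same item, "The summary of clinical benefit (ie, percentages of subjects with duration of disease control" of at least 4 months, in the disease control rate row. That row takes its methods from ORR, which is an exact binomial proportion.

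**The cut-off.** SAP 7.2 places the primary analysis after all subjects are enrolled and have had the chance to confirm a response following the first scan, "or up to 13 weeks of follow-up, whichever occurs first". SAP 7.3 adds a final analysis after long-term follow-up.

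**Scans and censoring.** The Protocol 1.3 imaging schedule is "Weeks 1 to 48: Q6W (± 1 week"), timed from first dose. Under SAP 5.2, DoDC runs from first dose and follows the PFS censoring rules. Appendix C censors a progression-free subject at the last evaluable scan.

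**Confirmation.** SAP Appendix B requires a CR or PR to be confirmed at least 28 days later. It allows unconfirmed responders to be counted (Interim_BOR) only in this setting: "At interim analyses (if any), due to lack of sufficient follow-up time for confirmation scan". SAP 7.1 lists no interim analysis.

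**The concern.** Four months is longer than the follow-up that the primary analysis guarantees. A simple proportion cannot tell a subject who progressed before 4 months from one who has not yet been followed that long. If both count as failures, the clinical-benefit rate partly measures how fast the trial enrolled. Two trials of the same drug, with the same true disease control, would then report different rates.

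The confirmed ORR has a milder form of the same problem. A subject whose first response appears at the second scan has no time to confirm it if enrolled near the end. The SAP recognises this and has a rule for it, but the rule does not reach the primary analysis.

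**Working it through.** **1. The plan's own figures.** SAP 3.2 states "Approximately 30 subjects will be enrolled in the study". Above 25% of 30 means at least 8 responders, and above 30% means at least 10. The binomial tails are 0.876 and 0.642 at a true ORR of 0.35, and 0.956 and 0.824 at 0.40. These match the stated 88%, 64%, 96% and 82%.

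**2. Timing.** The SAP duration formula is (days + 1) × 12 / 365.25.
- 13 weeks: 91 × 12 / 365.25 = 2.99 months.
- 4 months: 4 × 365.25 / 12 = 121.75 days = 17.4 weeks.
- Second scan at week 11, 12 or 13: 78, 85 or 92 × 12 / 365.25 = 2.56, 2.79 or 3.02 months.
- Third scan at week 17 or 18: 120 or 127 × 12 / 365.25 = 3.94 or 4.17 months.

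A progression-free subject with only the guaranteed follow-up is censored at 2.56 to 3.02 months and cannot show 4.

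**3. Size, by hand.** Take uniform accrual over A weeks, a 13-week cut-off and scans at exactly weeks 6, 12 and 18. The accrual period is assumed. A subject clear at week 12 reaches 4 months once the week-18 scan is in, whatever that scan shows. The share without that scan at the cut-off is (18 − 13)/A = 5/A. Counting censored subjects as failures therefore gives: simple rate = mature rate × (1 − 5/A). This ratio does not depend on the true rate, nor on whether the denominator is all subjects or only those with disease control.

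For the level, Protocol 2.3 reports a median PFS of 4.9 months in the earlier phase 2 study. With exponential PFS, the mature rate is 2^(−2.76/4.9) = 0.677, where 2.76 months is 12 weeks. Taking exact 4-month survival instead gives 2^(−4/4.9) = 0.568. The first is higher because progression is dated at the next scan.

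**4. Size, by simulation.** The same model, with the ±1-week scan windows and n = 30, has a mature rate of about 66%.

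| Accrual (assumed) | 1 − 5/A | Simple rate, by hand | Simple rate, simulated | Kaplan-Meier, simulated |
|---|---|---|---|---|
| 13 weeks | 0.62 | 42% | 37% | 63% |
| 26 weeks | 0.81 | 55% | 52% | 65% |
| 39 weeks | 0.87 | 59% | 57% | 65% |
| 52 weeks | 0.90 | 61% | 59% | 66% |

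A separate run gave 34% to 57% for the simple rate and 63% to 65% for Kaplan-Meier across 13 to 52 weeks, so the results agree to within about 3 points.

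**5. If censored subjects are dropped instead.** By hand the rate is 0.677(1 − 5/A) / (1 − 0.677 × 5/A), or 56%, 63%, 65% and 65% for the four accrual periods. It is closer to 68% but still low, because early progressors among late enrollees stay in while their progression-free peers drop out. Restricting the denominator to subjects with enough potential follow-up would avoid this. The answer depends on a rule that the SAP does not state.

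**6. ORR.** A first response at weeks 11 to 13 can be confirmed at weeks 15 to 17 at the earliest, or at the scheduled scan in weeks 17 to 19. Until then Table 14-2 scores it SD (for example C24, after an SD at the first scan). With a true ORR of 40% and 20% of responders first seen at the second scan (both assumed), the loss is 40 × 0.20 × 5/A points:
- 3.1 points at 13 weeks of accrual (0.9 responders of 30)
- 1.5 points at 26 weeks
- 1.0 point at 39 weeks (0.3 responders)
- 0.8 points at 52 weeks

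At the 13-week extreme, the probability of an observed ORR above 30% falls from 82% (true 40%) to 72% (true 36.9%).

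**The case against.** **The SAP never says that the percentage is crude.** This is correct. The reading rests on the figure being given in addition to the Kaplan-Meier landmarks and on its place in the Protocol's table. A reader might infer that the plan commits to a biased estimator. The documents support only that a simple proportion is the natural reading and that no rule for censored subjects is given.

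**A suitable analysis is already planned.** The Kaplan-Meier landmarks handle censoring, and their list is only an example, so 4 months could be added. That makes the repair easy, but the separate percentage would still be reported.

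**Few subjects are affected, at one analysis.** Thirteen weeks is the minimum for the last enrollee, not the follow-up of the whole trial. Only subjects enrolled in about the last 3 to 6 weeks are exposed, and the final analysis largely removes the shortfall. The concern is confined to the primary analysis.

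**It is descriptive.** SAP 2.2 says "No statistical hypotheses will be tested", so no decision error follows. The published figure can still mislead.

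**The ORR effect is small.** This stands. The exact 95% interval for 12 of 30 is 23% to 59%, far wider than 1 to 3 points, and the share of late responders is assumed.

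**The cut-off looks deliberate.** Thirteen weeks is the week-12 scan plus its window. A reader might conclude that it should move beyond the week-18 scan. That is a trade-off against delay, and it would not fully rescue a simple proportion, because a last scan at week 17 gives 3.94 months.

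**Conclusion.** The concern holds for the 4-month disease control figure at the primary analysis, on the condition that censored subjects count as not reaching 4 months. The simple rate is then low by a proportion of about 5/A. Under the assumed model that is about 34% to 57% against a mature 66%, while Kaplan-Meier stays within about 3 points. The direction and the dependence on accrual follow from the documents' own timing. The absolute rates rest on an assumed accrual of 13 to 52 weeks and on exponential PFS with the earlier study's median.

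The ORR point is secondary. The plan may understate the primary-analysis ORR slightly, by about 1 to 3 points on assumed inputs. The documents do not support saying that both rates are certainly biased low, or that the primary endpoint is materially compromised.

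**What to change.** 1. **SAP 9.5.2:** add 4 months to the listed DoDC landmarks. At the primary analysis, report that Kaplan-Meier estimate with its Greenwood interval in place of the simple percentage. State whether the denominator is all treated subjects or those with disease control. If a simple percentage is kept for the final analysis, state its rule for censored subjects.
2. **SAP 9.5.1 and Appendix B:** extend the existing Interim_BOR derivation to the primary analysis as a sensitivity analysis, shown beside the confirmed ORR, which remains the primary result.

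Both are SAP wording changes. They need no new data, no extra scans and no change to the cut-off.
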